Preventative treatments are especially important during the first five years post-menopause because women lose 2% of their BMD per year during this time. Calcium (Ca), vitamin D (D) and exercise are recommended for prevention of osteoporosis (5) and bisphosphonates (BPs) are prescribed to improve BMD in women with diagnosed osteoporosis (6). BPs may also be prescribed for women with low bone mass who are not yet osteoporotic, but are more controversial in this population due to the potential for adverse effects with their long-term use (7,8). Also, the best predictor of fracture is bone strength, and strength is determined by bone structure as well as BMD. While BPs are effective in improving bone density, findings on the effectiveness of BPs in improving bone structure are inconsistent (9). A bone loading exercise program (high-impact weight bearing and resistance training) promotes bone strength by improving bone structure and by promoting bone formation at sites of mechanical stress as well as by preserving BMD. This randomized controlled trial (RCT) will compare changes after 12 months in bone structure, BMD, and bone turnover in post-menopausal women with low bone mass randomized to one control and 2 treatment groups (N =103 per group): 1) optimal calcium + vitamin D (optimal CaD) alone (Control); 2) BP plus optimal CaD (Risedronate); and 3) a bone loading exercise program plus optimal CaD (Exercise). Bone-loading exercise programs for post-menopausal women with low bone mass may more effectively improve bone structure than either BPs or optimal CaD alone (9). Prescribing exercise programs and delaying use of BPs may prevent adverse effects from long-term use of BPs, and provide the opportunity for later use of BPs when they may be critically needed (8,15). Results of this study could be used in developing a clinical management pathway for women with low bone mass at their peak period of bone loss that would involve lifestyle modifications such as exercises prior to medications such as BPs.

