3 OBJECTIVES

3.1 *Study Objectives*

Our **long-term goal** is to contribute to the development of clinical practice guidelines for the promotion of bone health in postmenopausal women with low bone mass. Our **central hypothesis** is that improvements in bone health will be greater in subjects randomized to the Exercise group compared to subjects in either the Control or Risedronate groups.

Aim1: To compare Control, Risedronate, and Exercise group subjects on changes in bone structure at the tibia (bone strength index [BSI]: pQCT) and hip (femoral neck and shaft, intertrochanteric) (hipstructural analysis: [HSA: DXA]) at baseline, 6, 12 months.

H1a: At 12 months, there will be significantly greater improvements in bone strength index (BSI) at the 4% tibial site in Exercise subjects compared to subjects in either Risedronate or Control groups

H1b: At 12 months, there will be significantly greater improvements in bone mass distribution (HSA; centroid, mm) at the femoral neck in Exercise subjects compared to subjects in either Risedronate or Control groups

Aim2. To compare Control, Risedronate, and Exercise group subjects on changes in BMD at the total hip, femoral neck, and spine (DXA) at baseline, 6, and 12 months.

H2a: At 12 months, there will be significantly greater improvements in BMD at the total hip, femoral neck, and spine in Exercise and Risedronate subjects compared to subjects in the Control group

H2b: At least 80% of subjects in both the Exercise and Risedronate groups will have preserved BMD at the total hip, femoral neck, and spine.

Aim3: To compare Control, Risedronate, and Exercise group subjects on changes in bone formation and resorption at baseline, 6, 12 months. (formation: AlkphaseB, resorption: Serum NTx).

H3a: At 12 months there will be significantly greater decreases in serum markers of bone resorption (Serum NTx) in subjects in the Exercise and Risedronate groups compared to subjects in the Control group

H3b: At 12 months, mean Serum NTx levels for subjects in both Exercise and Risedronate groups will have decreased to levels considered at low risk for fracture (< 12.6 nmol BCE/L)

H3c: At 12 months, there will be significantly greater improvements in serum markers of bone formation (Alkphase B) in Exercise subjects compared to subjects in either Control or Risedronate group subjects

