10.3 Final Analysis Plan

Aim 1 hypotheses will be tested via RM-ANOVA models. Bone strength index at the tibia and bone mass distribution at the hip, the dependent variables of interest, will be measured at 6-month intervals (0, 6, and 12 months). A significant time*group interaction would indicate that the two groups being compared in each model have significantly different changes in bone structure over 12 months. Huynh-Feldt corrected F-tests will be used in order to account for any possible violation of sphericity. It is hypothesized that the exercise group will have significantly greater improvements than the control or risedronate groups. Up to 20% attrition may be expected over the course of the study, but we expect it

to be less due to the use of cognitive behavioral strategies by Research Project Coordinators (RPC), the Research Exercise Trainer (RET), and ETs to promote exercise adherence and retention in the study. The method of handling missing data is not likely to have an effect with small amounts of missing data. However, If there is a higher than expected attrition rate, a maximum likelihood estimation method (e.g. mixed models) will be used instead of RM-ANOVA in order to utilize all available data and not delete cases in a listwise manner.

Hypothesis 2a compares the groups changes in BMD and will also be analyzed using RM-ANOVA. Hypothesis 2b also involves BMD, but assesses the proportions of preservation of BMD in each group. It is expected that at least 80% of subjects in both the exercise+ and risedronate+ groups will have preserved BMD at the three skeletal sites, and that the control/CaD group will have a significantly lower proportion of participants preserving BMD over 12 months. In order to classify individuals into preserved vs. declined groups, change in BMD over 12 months will be compared to the least significant difference as defined by the Hologic DXA manufacturer for each respective skeletal site. Differences of proportion of preservation across groups will be assessed via chi-square tests, which would indicate if preservation of BMD was significantly different across groups. Aim 3 investigates the changes in bone formation and resorption over 12 months also using repeated-measures ANOVA. Alkphase B and Serum NTx will be measured at baseline, 6, and 12 months.

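### H2b sets an 80% target for BMD preservation and expects Control to be lower, but the planned chi-square tests across groups cannot judge the target and, if omnibus, do not compare Control with each active arm

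*Combined protocol and SAP*

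**What the plan says.** Section 3.1 states H2b as a numeric target: "At least 80% of subjects in both the Exercise and Risedronate groups will have preserved BMD", at the total hip, femoral neck and spine. That wording does not mention Control.

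Section 10.3 repeats the target as an expectation ("It is expected that at least 80% of subjects in both the exercise+ and risedronate+ groups will have preserved BMD") and adds that "the control/CaD group will have a significantly lower proportion of participants preserving BMD over 12 months". A woman is classed as preserved or declined site by site: "change in BMD over 12 months will be compared to the least significant difference as defined by the Hologic DXA manufacturer". The method is one sentence: "Differences of proportion of preservation across groups will be assessed via chi-square tests", "which would indicate if preservation of BMD was significantly different across groups".

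The plan gives no one-sample test or interval criterion against 80%. It names no contrast of proportions with Control, no direction, and no rule for combining the three sites. The power analysis in section 10.2 covers H1a only.

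**The concern.** The hypothesis and its test address different questions. H2b asks whether each active arm reaches a fixed level, and section 10.3 also expects Control to be lower. A chi-square test asks whether proportions are equal between groups. Its null hypothesis does not contain 80%, so neither a significant nor a null result bears on the target.

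If the test is a single comparison of all three groups, it also leaves open which groups differ and in which direction. It can be significant because Risedronate differs from Exercise, or because Control did best. An exercise arm no better than Control could then be reported as meeting H2b on the strength of the drug arm. A real success in both active arms could also be reported as a null result.

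**Working it through.** **Inputs from the documents.** Target 80% in each active arm (sections 3.1 and 10.3); 82 completers per group, 246 in all (section 10.2); alpha 0.05 (section 10.2, stated for H1a). The documents give no preservation rate for Control and no power for H2b, so the true rates used below are assumptions.

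**The plan's own figure.** For the H1a repeated-measures interaction, λ = f²·N·m/(1−ρ), df1 = (k−1)(m−1), df2 = (N−k)(m−1). With f = 0.10, m = 3, ρ = 0.5, k = 2 and N = 164: λ = 0.01 × 164 × 3 / 0.5 = 9.84, df 2 and 324, power 0.805. Then 164 × 1.5 = 246, as stated. Allowing for 20% attrition, 246/0.8 = 307.5, rounded up to 308, against 309 (3 × 103) planned. The sample size reproduces but says nothing about H2b.

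**Step 1: the chi-square and the 80% target.** Pearson chi-square on 3 × 2 tables, 82 per group, 2 df, so p = exp(−χ²/2). Intervals are exact (Clopper-Pearson).

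| Preserved: Exercise, Risedronate, Control | χ² | p | Active-arm 95% CI | Target |
|---|---|---|---|---|
| 78, 78, 78 (95.1% each) | 0 | 1.0 | 88.0-98.7% | clearly met |
| 53, 53, 37 (64.6%, 64.6%, 45.1%) | 8.55 | 0.014 | 53.3-74.9% | clearly missed |

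The test is null where the target is met and significant where it is missed. Pairwise tests do no better on this question: in the second row each active arm against Control gives p = 0.012.

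**Step 2: the omnibus test and Control.** Take 66, 66 and Control 78. The total is 210, so each group has 70 expected preserved and 12 expected declined. χ² = (4² + 4² + 8²)/70 + (4² + 4² + 8²)/12 = 1.37 + 8.00 = 9.37, p = 0.009. Both active arms are observed at 80.5% and the test is significant, but Control did best.

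**Step 3: a lenient reading of the plan.** Suppose H2b is called supported when the omnibus test is significant and both active arms are observed at 80% or more (at least 66/82). Assume true rates of Control 80%, Exercise 80%, Risedronate 95%, so that Exercise equals Control. Simulation at one site gives about 42%. Summing the product of the three binomial probabilities over all qualifying tables gives 41.5%. Adding the condition that Control is observed lowest leaves 31%. Requiring instead, in addition to the lenient rule, that Exercise be significantly above Control in its own two-group test (two-sided 0.05) leaves 2.5%.

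**Step 4: an observed 80% is not a demonstrated 80%.** 66/82 = 80.5% has exact 95% CI 70.3-88.4%. At a true rate of 78%, P(X ≥ 66) = 35% for one arm at one site. The lower limit first passes 80% at 73/82 (89.0%; lower limit 80.2%), whereas 72/82 gives 78.7%.

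**The case against.** **The test may not be omnibus.** The plan never uses that word, nor does it say three-group. The plural could mean one test per site, or pairwise tests, and for Aim 1 sections 10.2 and 10.3 do describe two-group comparisons. If pairwise tests were meant, significance plus the observed sign would address whether Control is lower. This stands as a limit on the second half of the point: a reader might infer that the plan certainly tests neither part, and the text does not support that much. The across-groups wording makes omnibus the natural reading. Even under the pairwise reading no contrasts are named, and the 80% target stays untested.

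**H2b itself contains only the 80% statement.** True of section 3.1. The Control statement appears only in section 10.3, as an expectation, but it is there as part of what the H2b analysis should show.

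**A more dramatic example is available but misleads.** With assumed true rates of Control 65%, Exercise 65%, Risedronate 90%, the omnibus test is significant in 99% of trials. A reader might infer that the plan would nearly always support H2b wrongly. It would not: at a true 65%, Exercise is observed at 66/82 or more only 0.16% of the time, so anyone who looks at the proportions would reject the claim. The 80/80/95 case in step 3 survives that check.

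**Requiring the lower limit to exceed 80% is only one defensible rule.** Accepted. The target can also be a descriptive benchmark, provided it is labelled so.

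**The endpoint is secondary, and H2a covers continuous BMD change.** Correct, and it limits the consequence. A reader might also infer that H2b carries a claim that exercise is equivalent to the drug; no section says so.

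**Conclusion.** The mismatch is real. That no between-group chi-square can judge the 80% target holds under any reading of section 10.3. That the analysis fails to show Control below each active arm holds if the test is omnibus. On that reading, and at one site with 82 per group, a lenient application would support H2b in about 42% of trials when Exercise truly equals Control at 80% and Risedronate is at 95%. Those rates are assumed for illustration and are not in the documents.

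The consequence is confined to a secondary hypothesis. The primary aim and N = 246 are unaffected.

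A reader might go further and argue that 80% would be easy to reach without treatment, because preservation is judged against the "least significant difference as defined by the Hologic DXA manufacturer" and the background says "women lose 2% of their BMD per year during this time". The documents do not establish this. They give neither the value of the threshold nor the spread of BMD change, the 2% is general background with no site named, and every Control participant receives calcium and vitamin D. It is not part of this conclusion.

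**What to change.** In section 10.3:

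1. Replace the across-groups chi-square with the Exercise-Control and Risedronate-Control differences in proportion preserved, each with a 95% CI, at each site.
2. Report each active arm's proportion with an exact 95% CI beside the 80% target, and do not call the target demonstrated from the observed proportion alone. Either require the lower limit to exceed 80% (73/82 at the planned size) or label 80% a descriptive benchmark.
3. State whether all three sites must be met jointly.

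This is a few lines of text and analysis, with no new data.

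Moving to contrasts with Control costs little power. With both active arms at 80% and Control assumed at 60%, 65% or 70%, one pairwise comparison (two-sided 0.05) has power 80%, 58% or 31%, against 86%, 63% or 33% for the omnibus test. Requiring both contrasts lowers this further.

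The larger cost comes with the lower-limit rule. P(X ≥ 73) is 0.697 at a true 90% and 0.881 at a true 92%:

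| Rule applied to | True 90% | True 92% |
|---|---|---|
| One arm, one site | 70% | 88% |
| Both arms, one site (squared) | 49% | 78% |
| Both arms, three sites, if independent (sixth power) | 11% | 47% |

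Sites within a woman are likely to be positively correlated, so the last row is a low bound. If the sponsor finds that bar too high, the descriptive label avoids it, but then no claim that 80% was shown should follow.

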Description of Intervention:	
This proposed study has a randomized 3-group (2 treatment groups & 1 control group), repeated measures experimental design. A computer generated code will be used to stratify subjects by exercise at baseline and then randomized to 3 groups (Control: n =103; Risedronate: n =103; Exercise: n =103) with assignments placed in sealed opaque envelopes for sequential use. All subjects will take dosages of calcium citrate supplements sufficient to ensure their total daily calcium (diet+supplements) is ~ 1200 mg daily and vitamin D³ supplements with daily dose to ensure serum levels of vitamin D [25 (OH)D] are between 30 ng/mL and 80 ng/mL(optimal CaD). Subjects randomized to the Risedronate group will take optimal CaD daily and 150mg of oral risedronate once monthly for 12 months but will not participate in the exercise program. Subjects randomized to the Exercise group will take optimal CaD and also participate in 12 months of a bone-loading exercise program three times weekly at a local community-based YMCA (Y). To ensure the bone outcomes were not due to the CaD supplementation, a group taking only optimal CaD will serve as a control. While only women in the exercise group will participate in the structured bone-loading exercise program developed for this study, all women will be encouraged to participate in exercises and will be informed of the benefit of weight bearing and resistance exercises. The primary outcome will be bone structure at the tibia and hip and secondary outcomes are bone mineral density (BMD) and bone turnover. Repeated measures of primary and secondary outcome variables will be conducted at baseline, 6 and 12 months to better understand response to intervention components with a

	maximum difference expected at 12 months. An exercise intervention lasting 12 months or 2 to 3 bone turnover (resorption / formation) cycles is necessary in order to measure the effects of training on bone outcomes.
Study Duration:	Time from subject enrollment to completion of analysis is 4 years and 6 months.
Subject Participation Duration:	Each subject will be asked to participate in the study for a total of 12 months.
Estimated Time to Complete Enrollment:	Study enrollment will begin in Year 1, month 6 and continue through Year 4, month 9.

SCHEMATIC OF STUDY DESIGN:

See [Protocol 1. Timeline for Data Collection](#), for details regarding collection of specific measures

Prior to
Enrollment

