Aim4: To explore relationships between adherence to exercise (%sessions attended) or adherence to risedronate (% pills taken) and changes in bone structure at the tibia (BSI) and hip (HSA).

3.2 *Study Outcome Measures*

3.2.1 *Primary*

Bone structure will serve as the primary outcome for this study and will be measured using peripheral quantitative computed tomography (pQCT) and Hip Structural Analysis (HSA) at baseline, 6 and 12M. PQCT will measure bone strength index (BSI) at the 4% and 66% tibial sites. BSI is based upon the total bone area, tissue density, bone porosity, and distribution or shape (moment of inertia) at that bone site and has been found to be a strong predictor of the torsion and bending strength of bones.⁽⁹⁾ Bone structure at the hip will be measured using HSA software and DXA testing.⁽¹⁰⁾ HSA specifically measures the distribution of bone mass at the hip. The data collected includes the cross-sectional area (CSA) occupied by bone mineral, an index of bone strength against compression; section modulus (Z, mm³), an index of bone strength against bending; and centroid (mm), the distance from the center of the mass to the periphery.^(10, 45)

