To promote optimal performance, participants will be provided the *Form 3. HOPS Exercise Booklet_Revised* and *Form 8. Exercise Log_Revised*. The booklet will include detailed written and visual supportive instructions for each exercise including specific prescribed exercise session parameters to guide the participants. The exercise log applies corresponding colors to associate exercises with those in the booklet. The exercise log will also be a tool used to detail the prescribed resistance, repetitions, sets, and steps to assure the participant is meeting the goals set forth for them by the study.

To promote optimal adherence and therapeutic potential of workload, a graphic feedback sheet will be provided to the participant (see *Protocol 9. Graphic Feedback*). The graphic feedback sheet will display graphs of the individual's prior performance relative to study goals in order to improve adherence. For statistical analysis, adherence will be defined as the % training sessions attended; this will be calculated using the participant logs, which will be validated by Y electronic entrance documentation.

Exercise participants can perform exercises at the Ys at any time during operating hours regardless of whether one of the study's on-site YET coordinators are present (*Protocol 10. Exercise Trainer Oversight Schedule_Revised*). Even when YET coordinators are not present, other exercise specialists at the Y will always be present to answer general exercise questions or assist if problems arise with the exercise equipment.

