Osteoporosis Knowledge Test Revised (*must be 1st questionnaire), *Form 21. Demographic Profile*, *Form 22. FRAX*, *Form 23. Screening Participants Contact Information Form* *_Revised*, *Form 24. Human Activity Profile Test (HAP)* and *Form 25. International Physical Activity Questionnaire (IPAQ)*(see *Protocol 25. Administering Osteo Knowledge Test* ; *Protocol 26. Administering FRAX*; *Protocol 27. Administering HAP Questionnaire*; *Protocol 28. Administering IPAQ*

6. Step 4: Reporting DXA Results

- a. Using the *Form 26. Bone Mineral Density Report*, report DXA results to participant.
 - i. *If DXA results indicate that the participant has either normal bone density, or that they are osteoporotic*, inform participant that they do not qualify for HOPS
 - E. Provide *Form 27. Calcium FAQ*, *Form 28. Vitamin D FAQ*, and *Form 29. Osteoporosis Pamphlet*
 - F. If the screener is osteoporotic, HOPS personnel can refer them to a provider for follow up using the *Protocol 29. Referral for Osteoporotic Screeners*.
 - G. Provide a flyer or two and ask participant to help spread the word about HOPS to friends and family.
 - H. The participant is now finished and may leave.
- b. *If the DXA shows that she has low bone mass (T score between-1 and -2.49), but not yet osteoporosis (T score < -2.5)*, the screening subject will be informed that they qualify for the next stage of screening, which includes a blood draw and blood pressure check.
- c. Confirm that screener wants to proceed with the next stage of screening and complete tasks outlined in #7: Step 5, immediately below.

7. Step 5: Blood Draw, BP, and concluding visit:

- a. *If the screener needs to have their blood drawn at the CRC*:
 - i. Take blood pressure using *Protocol 30. Checking Resting Blood Pressure* as a guide. Record results on Checklist.
 - ii. Discuss an approximate date/time for blood draw so that we know when to expect communication from the CRC.
 - iii. Hand them the following forms: *Form 30. CRC Qualification*, *Form 31. CRC Directions with Map*, *Form 32. Further Questions Contact Sheet* *_Revised* and *Form 29. Osteoporosis Pamphlet*
 - iv. Inform participant that we will contact them once we receive the results of their lab work, and at that point, will send a letter to their provider regarding participation in HOPS (see *Form 33. Provider Permission Letter* *_4*).
 - v. Allow participant to leave.

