7.2.2 Special Assays or Procedures

- Dual energy x-ray absorptiometry (DXA) at screening(baseline), 6M, 12M
 - Hip Structural Analysis at screening (baseline), 6M, 12M
 - Trabecular Bone Score at screening, 6M, 12M
- Peripheral quantitative computed tomography (pQCT) at baseline, 6M, 12M
- Estimated 1 repetition maximum (1 RM) at 2 weeks, 6M

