The relationships of interest in Aim 4 will be explored by assessing the correlations between percentage of sessions attended, percentage of risedronate pills taken, and 12-month changes in bone structure at the tibia and hip. Assuming the variables are normally distributed, Pearson correlations will be used. Spearman rank correlations will be used if any of the variables are found to be non-normal.

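### Aim 4 correlates non-randomised adherence with raw 12-month change and leaves baseline structure and baseline exercise unused, so the association is open to confounding in either direction and may be less precise than necessary

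*Combined protocol and SAP*

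**What the plan says.** Section 3.1 words Aim 4 as exploratory: "To explore relationships between adherence to exercise (%sessions attended) or adherence to risedronate (% pills taken) and changes in bone structure". It attaches no hypothesis, significance level or power to this aim.

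Section 10.3 gives the whole analysis: "assessing the correlations between percentage of sessions attended, percentage of risedronate pills taken, and 12-month changes in bone structure at the tibia and hip". On the statistic it says "Assuming the variables are normally distributed, Pearson correlations will be used", with Spearman as the fallback for non-normal variables. It names no covariate, partial correlation or regression, and does not say explicitly that each correlation is computed within one arm.

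Section 6.2 fixes the exercise measure: "For statistical analysis, adherence will be defined as the % training sessions attended". This is observed after randomisation.

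The baseline information is already there:
- Tibia (Section 7.2.2): "Peripheral quantitative computed tomography (pQCT) at baseline, 6M, 12M".
- Hip (Section 7.2.2): "Hip Structural Analysis at screening (baseline), 6M, 12M".
- Baseline exercise (Protocol Summary, Description of Intervention): "A computer generated code will be used to stratify subjects by exercise at baseline". The levels of this factor are not defined.
- Physical activity (Section 6.4.2): the HAP and IPAQ questionnaires are completed at the screening visit.

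**The concern.** Aims 1 to 3 compare randomised arms. Aim 4 does not: it asks whether women who attended more sessions, or took more tablets, changed more. Randomisation gives no protection there. Stratifying by baseline exercise balances the arms, but does nothing for a comparison of women inside one arm.

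Two separate issues follow.

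1. **Confounding.** If baseline exercise is related both to attendance and to bone response, the raw correlation mixes that relation with any dose-response. The same holds for baseline structure if it is related to adherence.
2. **Precision.** A change score contains the baseline value. Even if baseline structure is unrelated to adherence, leaving it out leaves removable variance in the outcome.

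Aim 4 is the only planned look at dose-response, in about 82 completers per active arm. A real relation could be diluted or an apparent one produced, when the variables needed to examine this are already on file.

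**Working it through.** **Inputs from the documents (Section 10.2 and Protocol Summary).** Significance level .05; correlation between time points rho = .5; f = .10; 3 time points; 82 completers per group; 20% attrition. The plan gives no sample-size figure for Aim 4.

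**The plan's own figure.** For the two-group time-by-group interaction, lambda = f² × N × m / (1 − rho) = .01 × 164 × 3 / .5 = 9.84, with 2 and 324 degrees of freedom. Power is 80.5%. Then 164 × 1.5 = 246, or 82 per group, and 82 / .8 = 102.5, rounded up to 103 per group (309 in all). The stated sizes reproduce, so n = 82 is used below.

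**What n = 82 can show.** The two-sided .05 threshold is 1.99 / sqrt(80 + 1.99²) = .217. By Fisher z, the correlation detectable with 80% power is .305. The .05 level is carried over as a yardstick, since Aim 4 sets none.

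**Baseline structure and precision.** With equal variances at the two visits, corr(baseline, change) = (rho − 1) / sqrt(2(1 − rho)), so baseline explains (1 − rho)/2 of the variance of change. The table takes a raw r of .25 with adherence unrelated to baseline; the partial r is .25 / sqrt(1 − share explained).

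| rho | corr(baseline, change) | Share explained | Partial r | Power raw → adjusted, n = 82 |
|---|---|---|---|---|
| .5 (plan) | −.50 | 25% | .289 | 62% → 75% |
| .7 (assumed) | −.39 | 15% | .271 | 62% → 69% |
| .9 (assumed) | −.22 | 5% | .256 | 62% → 64% |
| .95 (assumed) | −.16 | 2.5% | .253 | 62.2% → 62.8% |

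**Baseline structure and bias.** If adherence has no real effect, the spurious correlation is corr(adherence, baseline) × corr(baseline, change). For assumed adherence–baseline correlations of .1 to .5, it is −.05 to −.25 at rho = .5 and −.016 to −.079 at rho = .95. It is zero if adherence is unrelated to baseline structure.

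**Baseline exercise and bias.** Let a = corr(exercise, attendance), b = corr(exercise, change), and the true partial correlation be .30. The expected raw correlation is .30 × sqrt((1 − a²)(1 − b²)) + ab. The documents give neither a nor b; the values below are assumed.

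| Size of a and b | Opposite signs | Same signs |
|---|---|---|
| .2 | .288 − .04 = .25 | .288 + .04 = .33 |
| .3 | .273 − .09 = .18 | .273 + .09 = .36 |
| .4 | .252 − .16 = .09 | .252 + .16 = .41 |

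At .3 with opposite signs, Fisher z gives atanh(.183) × sqrt(79) − 1.96 = −.31, so power is about 38%. The adjusted analysis, aiming at .30, has about 78%.

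With no true effect, correlations of .3 with both variables give a spurious r of .09 and a false-positive rate of 12.6% instead of 5%. Correlations of .5 with both give .25 and 62%. If either correlation is zero, there is no bias.

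**The case against.** The strongest reply is that the aim is exploratory, with no hypothesis, alpha or power, and that simple correlations are a defensible description of it. That stands as to severity: nothing confirmatory rests on Aim 4. It is not a reason to leave collected baseline data unused.

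A reader might infer that the Aim 4 correlation is confounded. The documents do not support that. Confounding needs a baseline variable related to both adherence and change, and no section gives either relation. Stratifying on baseline exercise is a device to balance the arms, not evidence that exercise predicts attendance. That active women attend more and respond less is a plausible conjecture only, and the opposite sign inflates the correlation instead of diluting it.

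A reader might also infer that a true .30 would be missed. That is too strong: .18 is an expected value and would still pass the .217 threshold about 38% of the time.

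The precision argument leans on rho = .5, which Section 10.2 offers as a planning estimate. If repeat bone measures correlate at .9 or more, the gain is small.

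Finally, adjustment is only a partial cure. Injury or pain that stops exercise, drug discontinuation for side effects, and off-protocol bisphosphonates (Sections 2.3.1 and 5.4.1) can affect both adherence and bone. Adjusting for a baseline measured with error in a non-randomised comparison can itself add bias. These limits stand, and they govern how the result is labelled.

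**Conclusion.** The point holds as an optional improvement. Aim 4 as planned is unadjusted, its exposure is not randomised, and suitable baseline variables are available. The analysis is therefore open to confounding, of unknown size and sign, and may lose precision.

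The precision loss is material only if the between-visit correlation is near the plan's value. The confounding figures are illustrations resting entirely on assumed correlations; they show that moderate relations would be enough to matter at this sample size, not that such relations exist. For baseline structure, bias arises only if it is related to adherence; otherwise only precision is at stake. The sample size and Aims 1 to 3 are untouched.

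**What to change.** In Section 10.3, specify for Aim 4, separately within the Exercise and Risedronate arms:

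- A regression of the month-12 value (BSI at the 4% tibial site; femoral-neck HSA) on percentage adherence, the baseline value of the same measure, and the baseline-exercise stratum. Define the stratum's levels, or use the screening IPAQ score instead.
- If adherence is skewed, partial Spearman correlations with the same adjusters.
- The adjusted estimate with its 95% confidence interval, shown beside the raw correlation.
- A statement that both results are exploratory and associational, because causes of non-adherence that arise after randomisation, and measurement error in the baseline, are not removed.

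The cost is a short change of SAP wording, minor programming and a few degrees of freedom out of about 82 per arm. The exact number depends on how many stratum levels there are. No new data, visits or participants are needed. Fixing the adjusters now also avoids choosing them after the results are seen.
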